3.2 Site for Data Collection

The medical history collection, questionnaire, and anthropometric measurements of the enrolled patients will be conducted within the first week of the study, and then once each week at the 12th and 24th weeks. The questionnaire will be completed by specially trained staff. Stool and serum samples will be collected at weeks 0, 12th and 24th for intestinal flora and urotoxin determination. The routine biochemical indicators of the patients will be collected, including serum creatinine, urea nitrogen, albumin, prealbumin, hemoglobin, serum calcium, blood phosphorus, total parathyroid hormone, serum potassium, carbon dioxide, C-reactive protein, ferritin, transferrin saturation, et al.

3.3 Population

3.3.1 Participation Criteria

Inclusion criteria:

Investigators must maintain a screening log of all potential study candidates that includes limited information about the potential candidate, date, and outcome of the screening process (e.g. enrolled into study, reason for ineligibility, or refused to participate). After signing an informed consent form, potential patients must meet all of the criteria:

1. Age ≥ 65 years.
2. Receiving maintenance hemodialysis therapy for at least 6 months.

Exclusion criteria:

The following exclusion criteria must NOT be present for each subject:

1. Subjects with medical history that might affect oral feeding (e.g. intestinal obstruction, gastrointestinal bleeding, acute pancreatitis and accidental inhalation) within the last 1 month prior to screening.
2. Subjects with medical history that might affect gastrointestinal functions (e.g. inflammatory bowel disease (IBD), irritable bowel syndrome (IBS), short bowel syndrome (SBS), et al.).
3. Subjects who cannot communicate and collaborate normally.

3.3.2 The source and method of population selection.

The study will select the patients who are ≥ 65 years old and receive long-term hemodialysis treatment in the hemodialysis center, and their clinical manifestations should meet the eligible criteria. We will communicate with the patients about the content and significance of the study, and patients who agree to sign the informed consent will finally be included in the study.

3.3.3 Follow-up.

The schedule of follow-up visits is shown in the flowchart below.

The Study Flowchart

		Screening period	Introduction Period	Treatment Period 1 st to 12 th Week			Remedial Treatment Period (Only Group B) 13 th to 24 th Week		
		Follow-up 1	Follow-up 2	Follow-up 3	Follow-up 4	Follow-up 5	Follow-up 6	Follow-up 7	Follow-up 8
Follow-up Time Window		-4 th to -2 nd week	-2 nd to 0 week	4 th week	8 th week	12 th week	16 th week	20 th week	24 th week
Eligibility Criteria	Medical History	✓							
	Medicine Prescription	✓				✓			✓
	Hemodialysis Parameter	✓							
Signature of Informed Consent		✓							
Demographic Data		✓							
Kt/V			✓	✓	✓	✓	✓	✓	✓
URR			✓	✓	✓	✓	✓	✓	✓
3-Day Diet Records			✓			✓			✓
Height, Weight, BMI			✓			✓			✓
Upper Arm			✓			✓			✓

Circumference, Upper Arm Skin Fold Thickness								
Grip Strength (Non-Fistula Side)		√			√			√
Abdominal Fat		√			√			√
Body Composition Analysis (Bioresistive Method)		√			√			√
Nutritional Scores (SGA-7)		√			√			√
Life Quality Scores (SF-36)		√			√			√
Gastrointestinal symptoms (GSRS)		√			√			√
Enervation Frailty Scale (EFS)		√			√			√
Pittsburgh Sleep Quality Index		√			√			√
Scr		√	√	√	√	√	√	√
BUN		√	√	√	√	√	√	√
ALB		√	√	√	√	√	√	√
Prealbumin		√	√	√	√	√	√	√
Hb		√	√	√	√	√	√	√
Ca		√	√	√	√	√	√	√
P		√	√	√	√	√	√	√
iPTH		√			√			√
K		√	√	√	√	√	√	√
CO2 Binding Power		√	√	√	√	√	√	√
hs-CRP		√	√	√	√	√	√	√
Ferritin		√	√	√	√	√	√	√
Transferrin Saturation		√	√	√	√	√	√	√
Supply Postbiotics or Placebo		√	√	√	√	√	√	√
Intestinal Flora Determination		√			√			√
Urotoxin Determination		√			√			√

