3.3.3.1 Screening Period (-4th to -2nd week before the randomization)

According to previous study, we will screen the CKD-5HD patients who might meet the eligibility criteria. For patients who accept hemodialysis 3 times per week, the first follow-up visit of the screening period should be on the first hemodialysis day of the week (e.g. Monday or Tuesday). Prior to conducting any study procedures, informed consent should be obtained from the patient by the investigator. The patients can provide informed consents within 30 days before the screening procedures.

The following list summarizes the procedures for the screening period:

- We should record demographic information and medical history.
- We should record all medications used by the patient within last 4 weeks prior to the screening.
- We should perform a complete physical examination.
- We should record hemodialysis parameter, including type of vascular access route, current dialysis prescription and dry weight.
- We should record any problem of hemodialysis device, dialyzer and hemodialysis line.
- We should record the most recent URR and spKt/V of patients within last 1 month prior to the screening.
- We should review the eligibility criteria.
- The patients who meet the eligibility criteria after screening period should be divided randomly into the treatment group and control group.

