3.3.3.2 Introduction Period (-2nd to 0 week before the randomization)

The second follow-up visit should be on the first hemodialysis day of the week (e.g. Monday or Tuesday). The following list summarizes the procedures for the introduction period:

- We should record the most recent URR and spKt/V of patients within last 1 month prior to the randomization.
- We should record any change of medications after the last follow-up visit.
- We should record the diet of patients.
- We should score the rating scales listed in the flowchart above.
- We should perform the anthropometric measurements listed in the flowchart above.
- We should collect the results of recent routine blood test before dialysis of the patient.
- We should collect the blood and stool samples for urotoxins and intestinal flora baseline measurements.
- The patients will be divided randomly into treatment group and control group. Patients in the treatment group will be given oral intestinal flora metabolites 3 times a day and 1 bag each time. Patients in the control group will be given placebo.
- The therapeutic medications should be supplied.

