3.3.3.3 Treatment Period (1st to 12th Week)

Follow-up visits are scheduled at every 4 weeks in the treatment period. The following list summarizes the procedures for the treatment period:

- We should ask patients about any adverse events and changes in medication after last follow-up visit.
- We should record any change of dialysis prescription.
- We should record any problem of hemodialysis device, dialyzer and hemodialysis line.
- We should record the diet of patients in the 12th week.
- We should score the rating scales in the 12th week.
- We should perform the anthropometric measurements in the 12th week.
- We should collect the blood and stool samples for urotoxins and intestinal flora measurements in the 12th week.
- We should collect the results of recent routine blood test before dialysis of the patient in the 4th, 8th and 12th week.
- We should ensure whether the patient has still met the eligibility criteria. If so, supply the medicine at the original dose. If not, remove him/her from the group.

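### Exclusion 1 looks back only from screening, so it misses the 2–4 weeks before randomisation and gives no workable rule for the same events on trial

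*Protocol*

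**What the plan says.** **Entry.** Exclusion 1 (Protocol 3.3.1) covers medical history "that might affect oral feeding (e.g. intestinal obstruction, gastrointestinal bleeding, acute pancreatitis and accidental inhalation) within the last 1 month prior to screening". The heading of 3.3.3.1 reads "Screening Period (-4th to -2nd week before the randomization", so the look-back ends 2–4 weeks before week 0. The screening list includes "We should review the eligibility criteria". The introduction list (3.3.3.2, weeks -2 to 0) does not repeat it. The only update that list asks for on events since screening concerns drugs: "We should record any change of medications after the last follow-up visit". The flowchart in 3.3.3 ticks medical history at Follow-up 1 only.

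**On trial.** The treatment-period list (3.3.3.3) adds "We should ask patients about any adverse events and changes in medication after last follow-up visit" and then "We should ensure whether the patient has still met the eligibility criteria. If so, supply the medicine at the original dose". A patient who fails this check is to be taken out of the group. Section 3.3.3.4 repeats the rule for group B in weeks 13 to 24. Neither section offers a temporary stop.

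**Primary outcomes.** Section 3.4.1 builds them from physical examination, SGA-7, GSRS, TM-SF36 and EFS. Sections 3.3.3.2 to 3.3.3.4 and the flowchart place the scales and anthropometry at the introduction visit, week 12 and, for group B, week 24.

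**The concern.** By excluding patients with a recent obstruction, gastrointestinal bleed, pancreatitis or aspiration, the protocol treats these events as a reason not to start an oral product. The window is fixed to a visit that can be four weeks old at randomisation, and no later step is listed that would catch a new event.

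The same wording then has to serve the 4-weekly re-supply checks, where it does not work. One reading makes exclusion 1 inert. The other turns a bar that is temporary at entry into removal after randomisation. Sites in a multicentre open-label trial could choose differently. At stake are a small matter of patient safety and, on the second reading only, avoidable loss of primary data.

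**Working it through.** The plan states no figure for this point, so the check is date arithmetic and a comparison of the texts.

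**Inputs**
- Look-back: 1 month, ending at screening (3.3.1).
- Screening: week -4 to week -2, counted from randomisation at week 0 (3.3.3.1).
- Visits every 4 weeks, with supply from the introduction visit on (3.3.3.2 to 3.3.3.4 and flowchart).
- Planned size: 30 per group (3.6).
- Assumption: 1 month = 52.18/12 = 4.35 weeks.

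**1. Entry gap.** Gap = week of randomisation minus week of screening.
- Screening at week -4: 0 - (-4) = 4 weeks not covered, or 4/4.35 = 92% of the last month before randomisation.
- Screening at week -2: 0 - (-2) = 2 weeks not covered, or 2/4.35 = 46%.

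**2. Distance from the window's end to each supply visit.** Distance = visit week minus screening week.

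| Supply visit | Weeks since the window closed |
|---|---|
| Week 4 | 6–8 |
| Week 8 | 10–12 |
| Week 12 (group B) | 14–16 |
| Week 16 (group B) | 18–20 |
| Week 20 (group B) | 22–24 |

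An event after screening never falls in a window that ends at screening. A patient who passed exclusion 1 at screening therefore passes it at every later check, whatever has happened since.

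**3. The two readings at re-supply**
- *Literal:* exclusion 1 stays satisfied, so supply continues at the original dose after, for example, an aspiration. Nobody is removed and no data are lost through this criterion.
- *Month counted back from the visit:* the patient fails, and leaving the group is the only stated consequence.

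**4. What removal could cost.** The randomised comparison has one post-baseline assessment of the primary scales and anthropometry, at week 12. If removal ends visits, a patient removed at week 4 or 8 contributes 0 of 1. One such patient is 1/30 = 3.3% of an arm.

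**5. Does another step close the entry gap?**
- Section 3.2 describes history collection in enrolled patients in the first study week, but attaches no eligibility decision to it.
- Section 3.3.3.1 randomises those who meet the criteria after the screening period. A criterion whose window ends at screening gives the same answer later.
- Exclusion 2 has no time window and an open list, so it might catch the three gastrointestinal events. Its examples are chronic bowel disorders, and it does not naturally cover aspiration.

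**The case against.** Anchoring a look-back to screening is common drafting and is not an error in itself. The visit lists are summaries, and a clinician would probably not start, or would pause, a drink in a patient who has just bled or aspirated. The product is a food-standard beverage. The words about still meeting the criteria suggest that a current-status check was intended. All of this stands, and it keeps the point small.

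Four stronger inferences are tempting, but the documents do not support them.
- *That the entry gap biases the comparison.* It falls before allocation and affects both arms alike.
- *That the re-check as written loses primary data.* The loss needs the non-literal reading, and also that removal ends visits. Sections 3.3.3.3 and 3.3.3.4 do not say that follow-up stops.
- *That the protocol shows its intent by moving another look-back.* The introduction list does change "We should record the most recent URR and spKt/V of patients within last 1 month prior to the screening" into "We should record the most recent URR and spKt/V of patients within last 1 month prior to the randomization". Those are dialysis-adequacy values recorded at each visit, not eligibility criteria, so they show little about exclusion 1.
- *That the one-month window implies a one-month pause on trial.* The protocol gives no reason for the length of the window and does not use it after randomisation. A fixed minimum could withhold the product after feeding is already safe.

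It can also be said that removal after a failed re-check concerns every criterion. That is true. Exclusion 1 is still a clear case, because the events it names can resolve and at entry bar a patient only for a time. How removed patients are analysed may be settled in a statistical analysis plan that is not shown. Whether they stop product and whether they keep attending is for the protocol to say.

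**Conclusion.** The point holds as a cheap improvement, not as a threat to validity. On the literal text, exclusion 1 leaves 2–4 weeks before randomisation uncovered, equally in both arms, and no listed step repeats the eligibility check. After randomisation the criterion is either inert or, if a site counts the month back from the visit, leads only to removal. The possible loss of the week-12 assessment depends on that second reading and on removal ending visits.

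The size rests on randomisation at week 0 and on screening within its stated range. The documents give no rate for these events, so no count of affected patients can be given; practical harm is probably small.

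**What to change.** 1. In 3.3.1, let exclusion 1 cover the month before randomisation. In 3.3.3.2, add a line to confirm it at the introduction visit, directly before allocation.
2. In the re-supply bullets of 3.3.3.3 and 3.3.3.4, state that a patient with an exclusion 1 event on trial stops product or placebo from onset, not only from the next supply visit. The patient may resume the original dose when the treating clinician judges oral feeding safe, with no fixed minimum. The patient stays in follow-up, including the week-12 assessment, in the group as randomised.

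The cost is one changed phrase, one confirmation at an existing visit and one instruction in two sections. No test or visit is added. The downside is a few delayed entries and somewhat less exposure in patients whose product is paused.

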3.3.3.1 Screening Period (-4th to -2nd week before the randomization)

According to previous study, we will screen the CKD-5HD patients who might meet the eligibility criteria. For patients who accept hemodialysis 3 times per week, the first follow-up visit of the screening period should be on the first hemodialysis day of the week (e.g. Monday or Tuesday). Prior to conducting any study procedures, informed consent should be obtained from the patient by the investigator. The patients can provide informed consents within 30 days before the screening procedures.

The following list summarizes the procedures for the screening period:

- We should record demographic information and medical history.
- We should record all medications used by the patient within last 4 weeks prior to the screening.
- We should perform a complete physical examination.
- We should record hemodialysis parameter, including type of vascular access route, current dialysis prescription and dry weight.
- We should record any problem of hemodialysis device, dialyzer and hemodialysis line.
- We should record the most recent URR and spKt/V of patients within last 1 month prior to the screening.
- We should review the eligibility criteria.
- The patients who meet the eligibility criteria after screening period should be divided randomly into the treatment group and control group.

3.3.3.2 Introduction Period (-2nd to 0 week before the randomization)

The second follow-up visit should be on the first hemodialysis day of the week (e.g. Monday or Tuesday). The following list summarizes the procedures for the introduction period:

- We should record the most recent URR and spKt/V of patients within last 1 month prior to the randomization.
- We should record any change of medications after the last follow-up visit.
- We should record the diet of patients.
- We should score the rating scales listed in the flowchart above.
- We should perform the anthropometric measurements listed in the flowchart above.
- We should collect the results of recent routine blood test before dialysis of the patient.
- We should collect the blood and stool samples for urotoxins and intestinal flora baseline measurements.
- The patients will be divided randomly into treatment group and control group. Patients in the treatment group will be given oral intestinal flora metabolites 3 times a day and 1 bag each time. Patients in the control group will be given placebo.
- The therapeutic medications should be supplied.

3.3.3.3 Treatment Period (1st to 12th Week)

Follow-up visits are scheduled at every 4 weeks in the treatment period. The following list summarizes the procedures for the treatment period:

- We should ask patients about any adverse events and changes in medication after last follow-up visit.
- We should record any change of dialysis prescription.
- We should record any problem of hemodialysis device, dialyzer and hemodialysis line.
- We should record the diet of patients in the 12th week.
- We should score the rating scales in the 12th week.
- We should perform the anthropometric measurements in the 12th week.
- We should collect the blood and stool samples for urotoxins and intestinal flora measurements in the 12th week.
- We should collect the results of recent routine blood test before dialysis of the patient in the 4th, 8th and 12th week.
- We should ensure whether the patient has still met the eligibility criteria. If so, supply the medicine at the original dose. If not, remove him/her from the group.

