3.4 Outcomes

3.4.1 Primary Outcome Measure:

Outcome Measure	Measure Description	Time Frame
Changes of nutritional status from the baseline to the end of treatment and differences between the intervention group and the placebo group.	Nutritional status of the patient is defined as the results of physical examination and SGA-7 rating scale.	From the baseline to the end of treatment.
Changes of quality of life from the baseline to the end of treatment and differences between the intervention group and the placebo group.	Quality of life of the patient is defined as the scores of gastrointestinal symptom rating scale (GSRS), kidney disease life quality scale (TM-SF36) and enervation frailty scale (EFS).	From the baseline to the end of treatment.

3.4.2 Secondary Outcomes:

Outcome Measure	Measure Description	Time Frame
Changes of enterogenous urotoxin level from baseline to the end of treatment and difference between the intervention and placebo group.	Enterogenous urotoxin level is defined as the serum level of IS, PCS and TMAO. The levels of serum IS, PCS and TMAO will be measured by mass spectrometry.	From the baseline to the end of treatment.

Changes of intestinal flora structure from the baseline to the end of treatment, and the difference between the intervention group and the placebo group.
	
The structure of intestinal flora will be measured by the V3-V4 region of 16S rDNA with MiSeq PE300 sequencing platform for high-throughput analysis and described by number of the flora.
	
From the baseline to the end of treatment.

Changes of routine biochemical indicators from the baseline to the end of treatment, and differences between the intervention group and the placebo group.
	
The routine biochemical indicators include serum creatinine, urea nitrogen, albumin, prealbumin, hemoglobin, serum calcium, blood phosphorus, total parathyroid hormone, serum potassium, carbon dioxide, C-reactive protein, ferritin, transferrin saturation.
	
From the baseline to the end of treatment.

Changes of dietary intake from the baseline to the end of treatment, and the difference between the intervention group and the placebo group.
	
Dietary intakes of the patients will be described by the diet record.
	
From the baseline to the end of treatment.

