3.8 Statistical Analysis

Descriptive statistics for continuous variables will include questionnaire score, anthropometric and biochemical indicators, fecal flora structure and urotoxins level. They will be expressed as mean \pm standard deviation and median. Analysis of categorical variables will include frequency and percentage.

In analytical statistics, the distribution type of data will be initially considered when we determine the reference range, and then we will calculate the unilateral lower limit P5. We will compare the distribution of the variables between the normal population and the patients in the two groups with Independent t test, Chi-square test /Fisher exact test, one-way ANOVA and non-parametric analysis. We will analyze the relationship between exposure and outcome with Logistic regression and Cox

regression, including univariate and multivariate regression. In multivariate regression analysis, the selected variables include important general clinical data, the variables clearly associated with the outcome, and the variables analyzed as $P < 0.1$ in univariate regression.

Statistical analyses will be performed using Statistical Package for Social Science (SPSS) for Windows version 23.0 (SPSS Inc. Chicago, IL). Statistical mapping will be performed using GraphPad Prism v.8 (La Jolla, CA, USA) and R 4.1.0 (The R Foundation, Vienna, Austria). Sample size estimation will be performed using PASS 2021 (UT, USA).

$P < 0.05$ is considered statistically significant. All confidence intervals are stated at the 95% confidence level.

4. Subject Protection

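### Twelve of the 13 secondary biochemical outcomes are measured at baseline and weeks 4, 8 and 12, but section 3.8 names no baseline-adjusted or repeated-measures method, so it loses precision and early leavers' data

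*Protocol*

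**What the plan says.** **Schedule.** In the introduction period, section 3.3.3.2 takes the baseline laboratory values: "We should collect the results of recent routine blood test before dialysis of the patient". In the treatment period, section 3.3.3.3 adds three more: "We should collect the results of recent routine blood test before dialysis of the patient in the 4th, 8th and 12th week". The flowchart in section 3.3.3 ticks creatinine, BUN, albumin, prealbumin, hemoglobin, calcium, phosphorus, potassium, CO2, hs-CRP, ferritin and transferrin saturation at baseline and at weeks 4, 8 and 12. Only iPTH is restricted to baseline, week 12 and week 24.

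**Outcome.** Section 3.4.2 lists as a secondary outcome "Changes of routine biochemical indicators from the baseline to the end of treatment, and differences between the intervention group and the placebo group". This is a change over the treatment period, compared between arms.

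**Analysis.** Section 3.8 names "Independent t test, Chi-square test /Fisher exact test, one-way ANOVA and non-parametric analysis" for comparing variables between a normal population and the two patient groups. It then says "We will analyze the relationship between exposure and outcome with Logistic regression and Cox" regression. It names no paired test, no baseline-adjusted model for a continuous outcome and no repeated-measures method. It also does not say what the week-4 and week-8 values are for.

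**The concern.** The protocol collects four values per patient on 12 outcomes, and its listed methods make explicit use of at most two of them. Logistic and Cox regression do not suit continuous laboratory values unless these are first dichotomised or turned into event times. In practice that leaves a two-sample comparison at week 12.

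Two things are lost. First, a patient who gives blood at baseline, week 4 and week 8 and then leaves has no week-12 change and drops out of the comparison, although the data exist. Second, a raw change score is usually noisier than a comparison that adjusts for the baseline value. With about 30 patients per arm, both losses affect how much the laboratory outcomes can show.

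**Working it through.** **Inputs from the protocol**
- Visits: baseline and weeks 4, 8 and 12 (3.3.3.2, 3.3.3.3 and the flowchart).
- Indicators: 13 in section 3.4.2. All but iPTH are ticked at all four visits, so 13 − 1 = 12.
- Allocation 1:1 (3.1), 30 per group, 20% dropout by the end of the study (3.6).

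**Assumptions, because the protocol gives no figure**
- Correlation r between a patient's baseline and week-12 values: 0.4 to 0.7.
- Equal variance σ² at baseline and week 12.

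The protocol states no variance, correlation or precision for the laboratory outcomes, so there is no figure of its own to reproduce here.

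**Step 1. Is the simplest reading of the plan valid?** Take D = week-12 value minus baseline for each patient and compare D between arms with an independent t test. Each patient contributes one value, the arms are independent, and the test holds its nominal level. It also matches the outcome in 3.4.2. So the named test can be used correctly.

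**Step 2. How precise is it, compared with adjusting for baseline?** With complete data:
- Variance of the change score: 2σ²(1 − r)
- Residual variance of week-12 ANCOVA: σ²(1 − r²)
- Ratio: (1 − r²) / [2(1 − r)] = (1 + r)/2

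| r (assumed) | change score, σ² | ANCOVA, σ² | ratio |
|---|---|---|---|
| 0.4 | 2 × 0.6 = 1.20 | 1 − 0.16 = 0.84 | 0.70 |
| 0.5 | 2 × 0.5 = 1.00 | 1 − 0.25 = 0.75 | 0.75 |
| 0.7 | 2 × 0.3 = 0.60 | 1 − 0.49 = 0.51 | 0.85 |

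The standard error of the arm difference scales with the square root: √0.70 = 0.84 and √0.85 = 0.92. Confidence intervals are therefore about 16% narrower at r = 0.4 and 8% narrower at r = 0.7. With 30 × 0.8 = 24 completers per arm, the standard error falls from √(1.20 × 2/24) = 0.32σ to √(0.84 × 2/24) = 0.26σ at r = 0.4. At r = 0.7 it falls from √(0.60 × 2/24) = 0.22σ to √(0.51 × 2/24) = 0.21σ.

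**Step 3. What do weeks 4 and 8 add?** With complete data, a baseline-adjusted repeated-measures model with unstructured covariance gives essentially the week-12 ANCOVA result. The gain in step 2 therefore comes from baseline adjustment, not from the extra visits. Weeks 4 and 8 help the week-12 estimate through patients who leave early. At the stated dropout, up to 30 × 0.2 = 6 patients per arm could lack a week-12 value. A change-score test excludes all of them. The repeated-measures model keeps those who reached week 4 or week 8. The protocol does not say when dropouts are expected, so this part of the gain cannot be given a number.

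**The case against.** The strongest reply is that nothing here is wrong. Section 3.4.2 defines the outcome as a change from baseline to the end of treatment, and a t test on per-patient changes answers exactly that. Weeks 4 and 8 lie outside the defined contrast and come from routine clinical blood tests, so leaving them out of the comparison is a legitimate choice. The open-ended non-parametric entry in 3.8 could include paired rank tests. These are secondary outcomes in a trial that 3.6 calls exploratory, and an SAP that is not shown may already specify a longitudinal model.

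Most of this stands. The plan contains a valid analysis, and the absence of a longitudinal model from a protocol is not in itself a fault. What remains is narrower: 3.8 does commit to a list of methods, and for data already being collected a better one is available at almost no cost.

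A reader might go further and infer that the repeated draws will be tested as though they came from different patients, with a false-positive rate well above 5%. The protocol does not support this. No section pools visits. The presence of one-way ANOVA is not evidence for it either, because 3.8 ties the listed tests to a normal population and the two patient groups, which makes three groups without any comparison across visits. A reader might also credit the whole precision gain to averaging weeks 4, 8 and 12. That average is a different quantity from the week-12 difference that 3.4.2 calls for.

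**Conclusion.** The point holds as an improvement, not as an error. For 12 of the 13 secondary biochemical outcomes, the named methods allow a valid week-12 change comparison. That comparison leaves out weeks 4 and 8, excludes patients who leave before week 12, and has a larger variance than a baseline-adjusted analysis. The adjusted analysis has 0.70 of the change-score variance at r = 0.4 and 0.85 at r = 0.7, given complete data, equal variances at the two visits and an assumed correlation. The benefit from retaining early leavers is real but cannot be quantified from the protocol. Nothing here shows an inflated type I error, and the primary outcomes are not affected. If the SAP already specifies a baseline-adjusted longitudinal analysis, the point is closed by making 3.8 agree with it.

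**What to change.** In section 3.8, state that each laboratory outcome measured every four weeks will be analysed with a mixed model for repeated measures on weeks 4, 8 and 12. The terms are arm, visit, arm-by-visit interaction and baseline value, with an unstructured within-patient covariance. Report the arm difference at week 12 as the secondary outcome. State that any within-arm change will be tested with a paired method. iPTH has only one treatment-period value after baseline, so week-12 ANCOVA is its counterpart.

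The cost is a few lines of analysis wording and a little extra programming, with no new data or visits. The downside is that early leavers are handled under a missing-at-random assumption, which should be stated alongside the model.
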